The study population included senior students at XX Faculty of Nursing, University of XX, between February 2024 and May 2024 (N=95). Students who volunteered to participate were included in the sample without sample calculation. The inclusion criteria were (a) being 18 years of age or older, (b) being a fourth-year nursing student, (c) completing the data collection forms in full, and (d) volunteering to participate in the study. Being in the escape room for more than 6 minutes in each room was set as an exclusion criterion.

Hypothesis

H₁¹: Patient safety-themed escape room teaching method increases students' self-efficacy in patient safety practices in nursing students.

H₁²: Patient safety-themed escape room teaching method increases nursing students' satisfaction.

Data Collection Tools

As data collection tools in this research student Information Form, Patient Safety Self-Efficacy Questionnaire and Satisfaction with Training Methods were used. Informed consent was obtained from the students in the study, which was conducted on a voluntary basis.

Student Information Form

The form was developed by the researchers in line with the literature and consists of 5 questions to determine participants' demographic information, including age, gender, type of school they graduated from, and whether they have attended the elective course on patient safety.

Patient Safety Self-Efficacy Questionnaire

The structural content of the patient safety self-efficacy questionnaire created by the researchers was created with reference to Eskici et al. (Eskici et al., 2021). It includes a degree of competence between 0-75 (0=insufficient, 5=sufficient) for each goal. Fifteen headings were determined by matching the keywords in the 'International Patient Safety Goals' set by JCI (Table 1). These headings were finalised by consulting five experts in the field. A minimum score of 0 and a maximum score of 75 can be obtained from the questionnaire. High scores will indicate high self-efficacy for patient safety. Low scores would indicate low self-efficacy for patient safety.

Table 1. Patient Safety Self-Efficacy Headings

1. I can establish safe communication that can ensure patient safety.
2. I can cooperate with other disciplines for patient safety.
3. I can use reporting systems for patient safety.
4. I can make safe patient transfers.
5. I can determine the safe site when practicing giving injections to the patient.

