6. I can calculate the safe dose range in drug applications.
7. I can take the necessary security measures to verify patient identity.
8. I can use colour codes (red-white-blue-pink) in the hospital.
9. I can ensure patient privacy safely.
10. I can take precautions for falls in patient safety.
11. I can recognise the safe connections of medical materials given to the patient.
12. I can recognise applications that may infect the patient.
13. I can ensure the safety of medical supplies given to the patient in terms of infection.
14. I can recognise situations that may threaten patient safety related to the patient's environment.
15. I can take precautions for pressure injuries in patient safety.

Satisfaction with Training Methods Scale

The scale was developed by Gürpinar (Cronbach's alpha: 0.84) and used in their studies. It contains 16 propositions, with each proposition scored on a 5-point Likert scale (1=strongly disagree, 2=disagree, 3=undecided, 4=agree, 5=strongly agree). High average scores indicate that students' satisfaction with the education method is high. Low average scores indicate that

students' satisfaction with the education method is low. Students can rate their satisfaction with the training methods with a minimum of 16 and a maximum of 80 points.

Interventions

All participants who volunteered for the study were thoroughly briefed on the duration, flow, and expectations of the interventions. Both verbal and written consent were obtained from each participant. The date and time for the escape room activity were scheduled, and students were notified accordingly. Participants were required to assemble into teams of four to six members and report to the Nursing Simulation Laboratory within the designated time frame.

The Patient Safety Self-Efficacy Questionnaire was administered as a pre-test prior to the commencement of the escape room activity. The design and implementation of the escape room adhered to the 'Best Practice Standards' established by the International Nursing Association for Clinical Simulation and Learning (INACSL) Standards Committee and the INACSL Board of Directors (INACSL, 2016).

The intervention was structured in three phases: prebriefing, simulation training (Escape Room), and debriefing. Following the debriefing session, participants completed the Patient Safety Self-Efficacy Questionnaire and the Satisfaction with Training Methods Questionnaire.

Escape Room Design

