1. Calculation of a safe drug dose range.
2. Identification of different mother-infant patient wristbands.
3. Utilization of color codes (red, white, blue, pink) in the hospital setting.
4. Ensuring maternal privacy.
5. Addressing safety concerns with open incubator edges.

Third Room (Adult Intensive Care Unit):

- Students were asked to identify five practices that pose threats to patient safety:
 1. Incorrect connection of medical equipment (e.g., intravenous treatment administered through a nasogastric catheter).
 2. Presence of bloody and dirty peripheral catheter dressing.
 3. Oxygen mask tip exposed and in contact with the floor.
 4. Sharp objects present on the patient's bed.
 5. Patient cables and connections passing under the patient, risking pressure injuries.

C- Debriefing

- The debriefing phase utilized the Promoting Excellence and Reflective Learning in Simulation (PEARLS) method (Eppich & Cheng, 2015). This method encompasses four stages: reaction, definition, analysis, and summarization.

- During this phase, students engaged in reflective discussion about their experiences, including their practices, decision-making processes, and the outcomes of the simulation exercise. The aim was to facilitate a thorough understanding and learning from their simulation experience.

Legal and Ethical Aspects of the Research

Permission dated 18.04.2024 and numbered 27424 was obtained from XX University, XX Scientific Research Ethics Committee, as well as from the institution where the research was conducted. Informed Consent Forms were obtained from the participants. Permission to use the scale was granted.

Statistical Methods

The data obtained in the study were evaluated by using IBM SPSS Statistics for Windows, Version 22.0 (SPSS INC., Chicago, IL, USA) statistical software. Frequency and percentage analyses were used to determine the descriptive characteristics of the participants. Kurtosis and Skewness values were analysed to determine whether the research variables were normally distributed. Since the variables showed normal distribution, parametric methods were used in the analysis. Dependent groups t-test was used for the comparison of intragroup measurements. Independent groups t-test was used to compare quantitative continuous data between two independent groups.

Results

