According to participant information, the average age of the students was 23.5 years, with 69.6% being female. 84.8% graduated from Anatolian high schools, 8.7% from science high schools, and 6.5% from health vocational high schools. 43.5% had previously taken a patient safety course.

It was observed that students spent the most time in the escape room with information questions, averaging 2.59 minutes. They spent an average of 1.18 minutes in the second room

and 1.12 minutes in the third room. The average time for students to complete the escape room was 5.29 minutes (Table 2).

Table 2. Duration of Stay in Rooms

Rooms	Mean \pm SD
First room	2.59 \pm .85
Second room	1.18 \pm .21
Third room	1.12 \pm .32
Total time	5.29 \pm 1.4

Note. SD: Standard Deviation

The mean score of the Patient Safety Self-Efficacy Questionnaire before the application was 61.26. After the application, the score was 71.32, showing an increase of 10.06 points. The increase in score after the application was significant ($p < .05$). Students reported high satisfaction with the escape room training method, with a satisfaction score of 73.71 (Table 3).

Table 3. Comparison of Score Averages from Patient Safety Self-Efficacy Questionnaire Before and After the Escape Room

Groups	Mean \pm SD	t*	p
PSSE pre-test	61.26 \pm 13.43	-5.176	< .001
PSSE post-test	71.32 \pm 4.7		

Note. *: Paired sample t-test, PSSE: Patient Safety Self-Efficacy n: Number of participants, SD: Standard Deviation

When analyzing the effect of taking a patient safety course on self-efficacy evaluations in the patient safety-themed escape room training method, it was found that whether or not students had taken the patient safety course did not create a significant difference in self-efficacy pre-test and post-test scores ($p > .05$). In intragroup comparisons, a significant increase of 12.05 points was observed in students who had taken the patient safety course ($p < .05$). Similarly, a significant increase of 8.54 points was observed in students who had not taken the patient safety course ($p < .05$) (Table 4).

Table 4. Comparison of Score Averages from Patient Safety Self-Efficacy Test Before and After the Escape Room According to Patient Safety Course

Groups	Course taken (n=20)	Course not taken (n=26)	t ^a	p
	Mean ± SD	Mean ± SD		
PSSE pre-test	59.80 ± 16.96	62.38 ± 10.16	-.642	.524
PSSE post-test	71.85 ± 3.26	70.92 ± 5.64	.654	.516
t ^b	-3.412	-4.01		
p	.003	< .001		

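### Does Table 4 need a direct comparison of the two gains (12.05 and 8.54 points), with confidence intervals, to support what it says about the prior course?

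*Combined protocol and SAP*

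**What the plan says.** Statistical Methods names a paired t-test for changes within a group and, for comparisons between groups, says: "Independent groups t-test was used to compare quantitative continuous data between two independent groups". It names no test of change scores between groups, no interaction, no adjusted model and no confidence interval.

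Results opens the topic with "When analyzing the effect of taking a patient safety course on self-efficacy evaluations in the patient safety-themed escape room training method" and reports that "whether or not students had taken the patient safety course did not create a significant difference in self-efficacy pre-test and post-test scores". It continues: "In intragroup comparisons, a significant increase of 12.05 points was observed in students who had taken the patient safety course". The second gain is introduced as similar to the first: "a significant increase of 8.54 points was observed in students who had not taken the patient safety course".

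Table 4 is titled as a comparison of mean scores by course status. It prints means and SDs at both time points, the group sizes (20 and 26), two between-group t-tests and two within-group t-tests.

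The Hypothesis section has two hypotheses: that the method raises self-efficacy, and that it raises satisfaction. Neither mentions the prior course.

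**The concern.** The opening sentence can be read as asking whether a prior course changes how students respond to the escape room. On that reading the natural quantity is the difference between the two gains, or the post-test difference given the pre-test. Table 4 has neither. Two separate within-group tests cannot show whether gains are alike or different, and two cross-sectional p-values near .52 do not show which differences remain plausible.

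Two misreadings would be possible. A reader could take non-significance in groups of 20 and 26 as evidence that the course makes no difference. Or a reader could take 12.05 against 8.54 as evidence that it does.

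**Working it through.** **Inputs, all from Table 4.** Course taken (n = 20): pre 59.80 ± 16.96, post 71.85 ± 3.26, paired t = -3.412. Course not taken (n = 26): pre 62.38 ± 10.16, post 70.92 ± 5.64, paired t = -4.01. Differences below are course taken minus not taken.

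**1. Reproduce the printed tests.** Equal-variance t-test, df = 44, with SE = s_p × √(1/20 + 1/26).
- Pre-test: s_p = 13.52, SE = 4.022, t = -2.58/4.022 = -0.641, p = .525 (printed -.642, .524).
- Post-test: s_p = √[(19 × 3.26² + 25 × 5.64²)/44] = 4.761, SE = 1.416, t = 0.93/1.416 = 0.657, p = .515 (printed .654, .516).
- Gains: 71.85 - 59.80 = 12.05 and 70.92 - 62.38 = 8.54. Paired p = .0029 and .0005 (printed .003 and < .001).

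The small gaps are rounding. With Welch tests the between-group p-values are .55 and .49, so the choice of test does not matter.

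**2. Intervals for the printed differences (pooled).**
- Pre-test: -2.58, 95% CI -10.7 to 5.5.
- Post-test: 0.93, 95% CI -1.92 to 3.78 (Welch -1.74 to 3.60).

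**3. The contrast that is not printed.** SD of gain = gain × √n / |t|.
- Course taken: 12.05 × √20 / 3.412 = 15.79.
- Course not taken: 8.54 × √26 / 4.01 = 10.86.
- Check: combining the two groups implies an overall SD of gain of 13.19. Table 3 with n = 46 implies 10.06 × √46 / 5.176 = 13.18, so the reconstruction is sound.
- Difference in gain: 12.05 - 8.54 = 3.51. Welch SE = √(15.79²/20 + 10.86²/26) = 4.12, df = 32.1, p = .40, 95% CI -4.89 to 11.91. Pooled: p = .38, 95% CI -4.4 to 11.4.

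**4. Post-test difference adjusted for pre-test.** The SDs of gain imply pre-post correlations of .44 and .15 and a pooled slope of .084. Adjusted difference = 0.93 + .084 × 2.58 = 1.15, SE = 1.397, df = 43, p = .42, 95% CI -1.67 to 3.96.

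**5. What the extra contrasts add.** Of the 3.51-point difference in gain, 2.58 (2.58/3.51 = 74%) is the pre-test gap and only 0.93 is the post-test gap. Adjustment barely changes precision: the half-width is 2.82, against 2.85 unadjusted. Because the course preceded the pre-test, adjustment may also remove part of any course effect.

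**6. Set the wording against the figures.** The printed statement concerns pre-test and post-test scores, and both tests support it. The usual error is to find one group significant and the other not, and then to infer a difference. It does not occur here: both gains are significant and are presented as similar. No sentence says that the gains differ, or that they are equal.

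**The case for a change.** The strongest case for the concern is that the document raises the course-effect question itself, prints two unequal gains in adjacent sentences, and leaves the reader without a contrast or an interval. The omission is real. The data also could not support a claim of no effect. Power to detect a true difference of 3.51 points in gain is about 14%, and the difference detectable with 80% power is about 11 points. Had the text concluded that prior teaching makes no difference to the response, that would be an error. It does not.

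A further argument uses the scale limit ("A minimum score of 0 and a maximum score of 75 can be obtained from the questionnaire"). The post-test interval reaches 3.78 points, while only 75 - 70.92 = 4.08 points lie above the comparator mean, so the interval looks uninformative. That shows limited precision, but the 4.08 treats the comparator mean as known, and the documents give no meaningful difference by which to judge 3.78.

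Nor does the ceiling show that the upper part of the gain interval reflects baseline uncertainty alone. The cap of (75 - 59.80) - 8.54 = 6.66 points fixes the comparator gain. With both baselines fixed, letting the comparator post-test mean fall to its lower 95% limit (70.92 - 2.28 = 68.64) raises the cap to 15.20 - (68.64 - 62.38) = 8.94.

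Teamwork is a fair caveat: "Participants were required to assemble into teams of four to six members", and every interval here treats students as independent. The documents give neither an intraclass correlation nor team composition. As an assumption, take an intraclass correlation of 0.05 to 0.20 and course status constant within teams. The post-test half-width then becomes about 3.4 to 4.9 points with team-level degrees of freedom. With mixed teams the effect would be smaller or could reverse. The printed sentence is non-committal enough to stand either way.

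**Conclusion.** The concern does not hold. Table 4 compares scores by course status with the tests named in Statistical Methods, its figures reproduce, and the sentence drawn from it is accurate and limited to what was tested. The missing contrasts are 3.51 points for the gain (95% CI -4.9 to 11.9) and 1.15 points for the adjusted post-test score (-1.7 to 4.0). Both are non-significant and would change no number, inference or conclusion. The comparison belongs to neither hypothesis, and the Abstract, Discussion and Conclusion infer nothing from it. Intervals would tell an interested reader how little 46 students can settle, but that is a choice of presentation in an unhypothesised subgroup table.

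This rests on reconstruction from rounded summary figures, on two-sided 5% tests (inferred from the printed p-values) and on treating students as independent.
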